10.6 Appendix 6: List of Examples of Strong Cytochrome P450 3A Inducers

Strong CYP3A inducers include, but are not limited to, the following:

- St John's Wort extract
- apalutamide
- avasimibe
- carbamazepine
- enzalutamide
- ivosidenib
- lumacaftor
- mitotane
- phenobarbital
- phenytoin
- rifabutin
- rifampin
- rifapentine

10.7 Appendix 7: List of Examples of Strong Cytochrome P450 3A and P-glycoprotein Inhibitors

Strong CYP3A and P-gp inhibitors include, but are not limited to, the following:

- grapefruit juice
- atazanavir/ritonavir
- boceprevir
- clarithromycin
- cobicistat
- conivaptan
- cyclosporine
- danoprevir/ritonavir
- diltiazem
- erythromycin
- elvitegravir/ritonavir
- faldaprevir
- gemfibrozil/itraconazole
- glecaprevir
- idelalisib
- indinavir
- indinavir/ritonavir
- itraconazole
- ketoconazole
- lopinavir/ritonavir
- mibepradil
- mifepristone
- nefazodone
- nelfinavir
- paritaprevir/ritonavir/ombitasvir
- paritaprevir/ritonavir/ombitasvir/dasabuvir
- posaconazole
- ribociclib
- ritonavir
- saquinavir
- saquinavir/ritonavir
- simeprevir/odalasvir

- telaprevir
- telithromycin
- tipranavir/ritonavir
- troleandomycin
- voriconazole

10.8 Appendix 8: Numerical Pain Rating Scale

To be completed by the subject:

Numerical Pain Rating Scale

Please select the number that best describes your pain where you had your operation in the past 24 hours.

Subject Signature

Date (ddMmmYYYY)

Time

To be completed by site staff:

Please circle the visit day that this assessment was completed.

Day 1	Day 2	Day 3	Day 4
Day 5	Day 6	Day 7	Day 8
Day 9	Day 10	Early Termination	End-of-study

10.9 Appendix 9: Clinical Opiate Withdrawal Scale

For each item, circle the number that best describes the patient's signs or symptom. Rate on just the apparent relationship to opiate withdrawal. For example, if heart rate is increased because the patient was jogging just prior to assessment, the increase pulse rate would not add to the score.

Patient's Name: _____		Date and Time _____ / _____ / _____
Reason for this assessment: _____		
Resting Pulse Rate: _____ beats/minute Measured after patient is sitting or lying for one minute 0 pulse rate 80 or below 1 pulse rate 81-100 2 pulse rate 101-120 4 pulse rate greater than 120	GI Upset: over last 1/2 hour 0 no GI symptoms 1 stomach cramps 2 nausea or loose stool 3 vomiting or diarrhea 5 multiple episodes of diarrhea or vomiting	
Sweating: over past 1/2 hour not accounted for by room temperature or patient activity. 0 no report of chills or flushing 1 subjective report of chills or flushing 2 flushed or observable moisture on face 3 beads of sweat on brow or face 4 sweat streaming off face	Tremor: observation of outstretched hands 0 no tremor 1 tremor can be felt, but not observed 2 slight tremor observable 4 gross tremor or muscle twitching	
Restlessness Observation during assessment 0 able to sit still 1 reports difficulty sitting still, but is able to do so 3 frequent shifting or extraneous movements of legs/arms 5 unable to sit still for more than a few seconds	Yawning Observation during assessment 0 no yawning 1 yawning once or twice during assessment 2 yawning three or more times during assessment 4 yawning several times/minute	
Pupil size 0 pupils pinned or normal size for room light 1 pupils possibly larger than normal for room light 2 pupils moderately dilated 5 pupils so dilated that only the rim of the iris is visible	Anxiety or Irritability 0 none 1 patient reports increasing irritability or anxiousness 2 patient obviously irritable or anxious 4 patient so irritable or anxious that participation in the assessment is difficult	
Bone or Joint aches If patient was having pain previously, only the additional component attributed to opiates withdrawal is scored 0 not present 1 mild diffuse discomfort 2 patient reports severe diffuse aching of joints/muscles 4 patient is rubbing joints or muscles and is unable to sit still because of discomfort	Gooseflesh skin 0 skin is smooth 3 piloerection of skin can be felt or hairs standing up on arms 5 prominent piloerection	
Runny nose or tearing Not accounted for by cold symptoms or allergies 0 not present 1 nasal stuffiness or unusually moist eyes 2 nose running or tearing 4 nose constantly running or tears streaming down cheeks	Total Score _____ The total score is the sum of all 11 items Initials of person completing assessment: _____	

Score: 5-12 = mild; 13-24 = moderate; 25-36 = moderately severe; more than 36 = severe withdrawal

This version may be copied and used clinically.

10.10 Appendix 10: Protocol Version History

The Summary of Changes Table for Version 3 of the protocol is located directly before the Table of Contents.

Version 2: 14 Feb 2020

Section # and Name	Description of Change	Brief Rationale
Sponsor Signatory Page	Medical monitor's name and contact information changed	Administrative change
Section 1.1, Synopsis, Table 1-1 Section 1.3, Schedule of Activities, Figure 1-2 Section 3, Objectives and Endpoints, Table 3-1 Section 8.1.1.1, Time from End of Surgery to Time to Toleration of Solid Food and First Bowel Movement Section 9.4.5.1, Primary Efficacy Endpoint	“First” added before toleration of food in primary endpoint	Clarification
Section 1.1, Synopsis, Overall Design Section 4.1, Overall Design Section 6.3, Measures to Minimize Bias: Randomization and Blinding	“Primary” added before anastomosis after small and large bowel resection in randomization statement	Clarification
Section 1.1, Synopsis, Number of Patients Section 4.1, Overall Design	Number of screened patients changed from 680 to 425	Correction
Section 1.1, Synopsis, Concomitant Therapy Section 6.5, Prior Therapy and Concomitant Therapy	Strong cytochrome P450 3A (CYP3A) and P-glycoprotein (P-gp) inhibitors (eg, clarithromycin, diltiazem, grapefruit juice, indinavir, ketoconazole, ritonavir) added as prohibited prior and concomitant therapy	Request from regulatory agency
Section 1.1, Synopsis, Treatment Groups and Duration Section 1.2, Schema, Figure 1-1 Section 1.3, Schedule of Activities, Figure 1-2 Section 4.1, Overall Design	Description of when the End-of-study Visit will occur revised from 30 days after Day 10 to 30 days after Day 10 or after the day of discharge (whichever is sooner)	Clarification

Section 1.3, SOA, Figure 1-2 Section 8.2.6, Clinical Opiate Withdrawal Scale Section 9.4.6, Safety Analyses Section 10.9, Appendix 9, Clinical Opioid Withdrawal Scale	Clinical Opiate Withdrawal Scale (COWS) assessment added along with a description that the score in each domain will be summarized categorically	Request from regulatory agency to monitor patients for signs/symptoms of opioid withdrawal
Section 5.4, Screen Failures	Sentences added allowing rescreening of patients who met all entry criteria but whose surgery was rescheduled more than 14 days after signing the informed consent form (ICF) and stating that these patients must resign the ICF if the rescheduled surgery is more than 14 days after the originally-scheduled surgery and the medical monitor should be contacted to see if any screening tests will need to be repeated	Administrative change to allow patients who met the entry criteria to participate in the study even though their surgeries were rescheduled
Section 6.5, Prior Therapy and Concomitant Therapy	Wording for prohibited medications revised from up to end of treatment to through the end of study treatment	Clarification
Section 6.5, Prior Therapy and Concomitant Therapy Section 9.4.3, Prior and Concomitant Therapies	Sentences added citing the 4 enhanced recovery protocol elements that must be captured in the electronic case report form (eCRF) and that the investigator should determine the appropriate management of patients with signs/symptoms of opioid withdrawal, severe hypersensitivity to study treatment, and gastrointestinal perforation; statistical analyses modified to state that elements of the enhanced recovery protocol will be listed for each patient and summarized	Request from regulatory agency
Section 7.1, Discontinuation of Study Treatment	Sentence added that the investigator should consider	Request from regulatory agency to add specific

	discontinuation of study treatment if opioid withdrawal is suspected, and that study treatment must be discontinued if patients have a COWS score > 36, severe hypersensitivity thought to be related to study treatment, or signs/symptoms of gastrointestinal perforation	guidance regarding discontinuation in specific situations
Section 8.1.1.1, Time from End of Surgery to Time to Toleration of Solid Food and First Bowel Movement Section 9.4.3, Prior and Concomitant Therapies Section 9.4.5.1, Primary Efficacy Endpoint	Sentence added to record the reason for discharge prior to having the first bowel movement in the eCRF and text and e-mail added as ways to contact the investigator within 24 hours of the first bowel movement after discharge; statistical analyses modified to state that the reason for discharge prior to having the first bowel movement will be listed	Request from regulatory agency (reason for discharge); administrative change (provision for text and e-mail communication contact)
Section 8.1.2.2, Reinsertion of the Nasogastric Tube	“Postoperative” added to define when to capture reinsertion of the nasogastric tube	Clarification
Section 8.2.5, Numerical Pain Rating Scale	Phrase specifying pain to be assessed once daily in the morning at approximately the same time of day added	Clarification
Section 8.3.1, Time Period and Frequency for Collecting Adverse Event and Serious Adverse Event Information Section 8.3.2, Method of Detecting Adverse Events and Serious Adverse Events	Sentence referencing Appendix 3 for information about recording, evaluating, and assessing causality of adverse events and serious adverse events moved from Section 8.3.1 to 8.3.2	Clarification
Section 9.4, Statistical Analyses	Table 9-1 added to show how protocol study days will be mapped to analysis study days	For programming and analysis purposes to ensure compliance with CDISC requirements
Section 9.4.7.1.3, Exposure-response Analysis	Section added that an exploratory exposure-response analysis will be conducted for	Clarification

	efficacy and safety and reported in a separate pharmacokinetic report	
Section 10.2, Appendix 2: Clinical Laboratory Tests	International normalized ration (INR) added to clinical chemistry	Addition to ensure consistency with revised liver safety criteria in Section 10.5
Section 10.3.3, Reporting of Serious Adverse Events	Fax added as a way to report a new serious adverse event or update data on a serious adverse event after electronic data capture is taken offline	Administrative change
Section 10.5, Appendix 5: Liver Safety: Suggested Actions and Follow-up Assessments	Alanine aminotransferase (ALT) $\geq 3 \times$ upper limit of normal (ULN) was revised to ALT or aspartate aminotransferase (AST) $> 8 \times$ ULN for the liver chemistry study treatment stopping criteria; bilirubin was revised to total bilirubin, ALT or AST $\geq 3 \times$ ULN AND bilirubin $\geq 2 \times$ ULN ($> 35\%$ direct bilirubin) OR international normalized ratio (INR) > 1.5 was revised to ALT or AST $> 3 \times$ ULN AND total bilirubin $< 2 \times$ ULN or INR ≤ 1.5 , and ALT $\geq 3 \times$ ULN AND bilirubin $\geq 2 \times$ ULN or INR > 1.5 was revised to ALT or AST $> 3 \times$ ULN AND total bilirubin $> 2 \times$ ULN or INR > 1.5 under the monitoring actions; and a flowchart was added	Requested by regulatory agency
Section 10.7, Appendix 7: List of Examples of Strong Cytochrome P450 3A and P-glycoprotein Inhibitors	List of strong CYP3A and P-gp inhibitors added	Requested by regulatory agency
Section 10.8, Appendix 8: Numerical Pain Rating Scale	Numerical Pain Rating Scale added	Clarification

10.12 Appendix 12: Abbreviations and Acronyms

ADL	activities of daily living
AE	adverse event
ALP	alkaline phosphatase
ALT	alanine aminotransferase
ASA	American Society of Anesthesiologists
AST	aspartate aminotransferase
AUC	area under the plasma concentration-time curve
AUC _{0-last}	area under the plasma concentration-time curve from time zero to the time of the last quantifiable concentration after dosing
AUC _{0-τ}	area under the concentration-time curve over the dosing interval τ (12 hours) on Day 3, calculated by Linear Up/Log Down Trapezoidal Method
BID	twice daily
BLQ	below the lower limit of quantification
CFR	Code of Federal Regulations
CIOMS	Council for International Organizations of Medical Sciences
CI	confidence interval
CL/F	apparent total clearance estimated according to: $CL/F = \text{Dose}/AUC_{0-\tau}$ on Day 3 (for naldemedine only)
C _{max}	maximum observed plasma concentration on Day 3
COWS	Clinical Opiate Withdrawal Scale
CPK	creatinine phosphokinase
CRF	case report form
CRO	contract research organization
CTCAE	Common Terminology Criteria for Adverse Events
CV	coefficient of variation
CYP	cytochrome P450
DMC	Data Monitoring Committee
ECG	electrocardiogram
eCRF	electronic case report form
ED ₅₀	amount of drug that produced the desired effect in 50%
EDC	electronic data capture
ET	early termination
GCP	Good Clinical Practice
GI	gastrointestinal
GI2	time from end of surgery to time to first toleration of solid food and first bowel movement
HBcAb	hepatitis B core antibody
HBsAg	hepatitis B surface antigen
HIPAA	Health Information Portability and Accountability Act
HPLC	high performance liquid chromatography
ICF	informed consent form

ICH	International Council for Harmonisation of Technical Requirements for Pharmaceuticals for Human Use
IgG	immunoglobulin G
IgM	immunoglobulin M
INR	international normalized ratio
IRB	Institutional Review Board
IWRS	Interactive Web Response System
KM	Kaplan-Meier
LDH	lactate dehydrogenase
Mean	arithmetic mean
MedDRA	Medical Dictionary for Regulatory Activities
mITT	Modified Intention-to-Treat
MME	morphine milligram equivalent
MR _{M/U, AUC}	metabolic ratio of AUC _{0-last} of nor-naldemedine to AUC _{0-last} of naldemedine, corrected for molecular weight, defined as (nor-naldemedine AUC _{0-last})/(naldemedine AUC _{0-last}) × (naldemedine molecular weight [570.64])/(nor-naldemedine molecular weight [516.55]) (for nor-naldemedine only)
MR _{M/U, C_{max}}	metabolic ratio of C _{max} of nor-naldemedine to C _{max} of naldemedine, corrected for molecular weight, defined as (nor-naldemedine C _{max})/(naldemedine C _{max}) × (naldemedine molecular weight [570.64])/(nor-naldemedine molecular weight [516.55]) (for nor-naldemedine only)
N	number of non-missing observations
NPRS	Numerical Pain Rating Scale
ODT	orally disintegrating tablet
OIC	opioid-induced constipation
PAMORA	peripherally acting mu-opioid receptor antagonist
P-gp	P-glycoprotein
PK	pharmacokinetic(s)
postop	postoperative
RBC	red blood cell
RMST	restricted mean survival time
SAE	serious adverse event
SAP	statistical analysis plan
SD	standard deviation
SoA	schedule of activities
SUSAR	suspected unexpected serious adverse reaction
TEAE	treatment-emergent adverse event
T _{max}	time to maximum plasma concentration on Day 3
ULN	upper limit of normal
US	United States
WBC	white blood cell
WHO-DD	World Health Organization Drug Dictionary
WOCBP	woman of childbearing potential

## RECORDS ON REVISIONS

### Document History

Version Number	Date
1	2 July 2020

## LIST OF ABBREVIATIONS AND DEFINITIONS OF TERMS

ALT	alanine aminotransferase
ANCOVA	analysis of covariance
AST	aspartate aminotransferase
AUC	area under the concentration-time curve
BLQ	below the limit of quantification
CI	confidence interval
C max	maximum observed plasma concentration
CL/F	apparent total clearance
COVID-19	Coronavirus disease 2019
COWS	clinical opiate withdrawal scale
CV	coefficient of variation
DEC	decrease
DMC	data monitoring committee
ET	early termination
CRF	case report form
INC	increase
INR	international normalized ratio
KM	Kaplan Meier
mITT	Modified Intention-to-treat
MedDRA	Medical Dictionary for Regulatory Activities
MME	morphine milligram equivalent
MR M/U	metabolic ratio
NPRS	numerical pain rating scale
PK	Pharmacokinetic
PK-C	pharmacokinetic concentration
PK-P	pharmacokinetic parameter
PPS	Per-protocol Set
PT	preferred term, prothrombin time
RMST	restricted mean survival time
SAP	statistical analysis plan
SD	standard deviation
SOC	System Organ Class
STEAE	Serious treatment-emergent adverse event
TEAE	treatment-emergent adverse event
TFL	table, figure, and listing
T max	time to maximum plasma concentration

ULN                    upper limit of normal  
WHO-DD                World Health Organization Drug Dictionary

## 1. INTRODUCTION

This statistical analysis plan (SAP) describes the statistical methods and data handlings to be employed for the analysis of the study protocol 1902G1721, Version 3, dated 18 June 2020. Table, figure, and listing (TFL) mock-ups are provided in the TFL shells prepared separately.

All the analyses described in the SAP will be performed in the Biostatistics Center, Biometrics, Shionogi Inc. Any deviations from the final SAP will be documented in the clinical study report.

## 2. OVERVIEW

This is a Phase 2, multicenter, randomized, parallel-group, double-blind, placebo-controlled study in patients undergoing partial small or large bowel resection with primary anastomosis or radical cystectomy requiring bowel transection with primary anastomosis.

The study will consist of 3 study periods:

- a Screening/Baseline period (Day -14 to Day 0)
- a Treatment period (study treatment for no more than 11 days, including Day 0 [day of surgery] plus through 10 postoperative days).
- a Follow-up period 30 days after Day 10 or after the day of discharge (whichever is sooner), with a window of + 3 days, but not < 30 days (End-of-study Visit) or an Early Termination (ET) Visit.

## 3. STUDY OBJECTIVES

### 3.1 Primary Objective

The primary objective of this study is:

- To compare the efficacy of naldemedine 1.25 mg, 2.5 mg, and 5 mg and placebo for the primary endpoint.
  - The primary endpoint is the time from the end of surgery to time to first toleration of solid food and first bowel movement (GI2).

### 3.2 Secondary Objective

The secondary objective of the study is:

- To compare the efficacy of naldemedine 1.25 mg, 2.5 mg, and 5 mg and placebo for the secondary endpoints.
  - Secondary endpoints are the time from the end of surgery to time when the discharge order is written, proportion of patients requiring postoperative reinsertion of the nasogastric tube, proportion of patients with nausea on Days 1 through 3, proportion of patients with vomiting on Days 1 through 3 and

proportion of patients discharged by Day 10 who are readmitted for any reason within 30 days after discharge from the hospital.

### **3.3 Other Objectives**

- To compare the efficacy of naldemedine 1.25 mg, 2.5 mg, and 5 mg and placebo for the exploratory endpoints
- To characterize the pharmacokinetics (PK) profile of naldemedine 1.25 mg, 2.5 mg, and 5 mg and its metabolite (nor-naldemedine) for the PK endpoints.
- To compare the safety of naldemedine 1.25 mg, 2.5 mg, and 5 mg and placebo for the safety endpoints

## **4. STUDY DESIGN**

### **4.1 Study Blinding and Randomization**

Eligible patients will be randomized in a ratio of 1:1:1:1 to one of the following treatment groups: naldemedine 1.25 mg, 2.5 mg, or 5 mg or placebo. Randomization will be stratified by the planned surgical procedure, ie, small bowel resection with primary anastomosis, large bowel resection with primary anastomosis, or radical cystectomy requiring bowel transection with primary anastomosis. All patients will be centrally randomized to study treatment using an Interactive Web Response System (IWRS).

### **4.2 Sample Size**

The sample size of between 44 and 85 per group will be required for the Modified Intention-To-Treat (mITT) Population to provide at least 80% power. The simulation estimated 44 patients per treatment group to see a linear trend in the restricted mean survival time (RMST) up to 240 hours for the time to the event of GI2 in across a 24-hour difference between naldemedine 5 mg and placebo under 80% statistical power at a 2-sided significance level of 0.05. Eighty-five patients per treatment group will be required to see a linear trend in RMST up to 240 hours across an 18-hour difference between naldemedine 5 mg and placebo. The final sample size will be dependent on the enrollment rate during the fixed enrollment period. A minimum of 44 patients per group in the mITT population is desired.

## **5. ANALYSIS POPULATIONS**

### **5.1 Modified Intention-to-treat Population**

The mITT Population will include all randomized patients who received at least 1 dose of study treatment and had at least 1 postbaseline efficacy assessment for the primary efficacy endpoint, which includes all three components (end of surgery time, time when the patient first tolerates solid food, and time of first bowel movement) of the time to event of GI2. Patients will be analyzed according to the treatment to which they were randomized.

This population will be the primary efficacy analysis population.

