8.1 Efficacy Assessments

8.1.1 Primary Efficacy Assessments

8.1.1.1 Time from End of Surgery to Time to First Toleration of Solid Food and First Bowel Movement

The time from the end of surgery (defined as the time the patient leaves the operating room) to time to first toleration of solid food (defined as the time when the patient consumes a meal that requires chewing and has no significant nausea or vomiting, as per the judgment of the investigator, for 4 hours after that solid food) and first bowel movement (GI2) will be recorded in the eCRF. First toleration of solid food and first bowel movement will be recorded until the patient meets the primary endpoint described above. If the patient discontinues study treatment, the patient still needs to be followed for GI2 until the achievement of this endpoint or until he/she completes the study. If the patient is withdrawn from the study, first toleration of solid food and first bowel movement, as applicable, will be recorded at the ET Visit (see also [Section 9.4.5.1](#)). If a patient is discharged from the hospital prior to having a first bowel movement, the reason for discharge prior to having the first bowel movement will be recorded in the eCRF. Additionally, the patient will be instructed to inform the investigator or qualified designee by phone, text, or e-mail within 24 hours of having a first bowel movement up to and including Day 10. The investigator or qualified designee will communicate (phone, text, or e-mail) with the patient daily up to and including Day 10 to record when the first bowel movement occurred.

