9.4.5.1 Primary Efficacy Endpoint

The primary endpoint will be time from the end of surgery (defined as the time the patient leaves the operating room) to time to first toleration of solid food (defined as the time when the patient consumes a meal that requires chewing and has no significant nausea or vomiting, as per the judgment of the investigator, for 4 hours after that solid food) and first bowel movement (GI2).

The mean survival time, which is also referred to as the RMST, of GI2 events within 240 hours will be estimated using the area under the Kaplan-Meier (KM) curve. To demonstrate the linear dose-response relationship between treatment groups (3 naldemedine groups and placebo group) and the RMST, the linear contrast test for trend with contrast coefficients of (-3, -1, 1, 3) will be performed. If a dose-response relationship is detected, then pairwise comparisons of the RMST between each dose group of naldemedine and the placebo group will be conducted, and the treatment differences (with its 95% confidence interval [CI]) will be provided. If an event does not occur during the evaluation period of 240 hours, the patient will be censored at the time of his/her last nonmissing postbaseline assessment. The same analysis will be performed in the Per Protocol set. In addition, the reason for discharge prior to having the first bowel movement will be listed.

Patients will continue to be evaluated for efficacy regardless of treatment adherence. The use of additional therapies or interventions that could treat any component of the primary endpoint (eg, motility agents, anti-emetics, laxatives, etc), may confound the results of the primary efficacy analysis. This list of therapies will be finalized before database lock. To examine this issue, the following exploratory analyses of the GI2 endpoint will be performed or provided:

- Repeat of the primary analysis, excluding all patients who received additional therapies at any time postrandomization that could treat any of the components of the GI2 endpoint. It is recognized that this subset is selected based on postrandomization decisions, may be confounded with the treatment group, and may not represent a randomized subgroup of the primary endpoint.
- Table of proportion of patients in each treatment group who received additional therapies that could treat any of the GI2 components.

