## 6.4 Missing Data

Missing values will not be imputed. All statistical analyses will be based on observed cases unless otherwise noted.

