### 9.1 Primary Endpoint

The time from the end of surgery (defined as the time the patient leaves the operating room) to time to first toleration of solid food (defined as the time when the patient consumes a meal that requires chewing and has no significant nausea or vomiting, as per the judgment of the investigator, for 4 hours after that solid food) and first bowel movement (GI2) will be the primary endpoint and called "Time to event of GI2". The time to event of GI2 will be the later time at which all of the following criteria are met:

- First toleration of solid food (as defined above)
- First bowel movement after surgery

If one of three time components (end of surgery time, time when the patient first tolerates solid food, and time of first bowel movement) is missing, time to event of GI2 will be considered as missing.

If time to event of GI2 does not occur during the evaluation period of 240 hours, the patient will be censored at the time of his/her last nonmissing postbaseline assessment.

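### SAP 5.1 and 9.1 do not say whether a blank food or bowel-movement time means censoring or removal from the primary analysis

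*SAP*

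**What the plan says.** Protocol 9.3 defines the mITT as randomized patients with at least one dose and at least one postbaseline assessment for the primary endpoint. SAP 5.1 repeats this and adds "which includes all three components (end of surgery time, time when the patient first tolerates solid food, and time of first bowel movement").

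SAP 9.1 defines GI2 as the later of two events: "The time to event of GI2 will be the later time at which all of the following criteria are met". Two rules follow. If one of the three times "is missing, time to event of GI2 will be considered as missing". And: "If time to event of GI2 does not occur during the evaluation period of 240 hours, the patient will be censored" at the last nonmissing postbaseline assessment. SAP 6.4 sets the default: "All statistical analyses will be based on observed cases unless otherwise noted".

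Protocol 9.4.5.1 has only the second rule: "If an event does not occur during the evaluation period of 240 hours, the patient will be censored". Protocol 8.1.1.1 says that after stopping study treatment "the patient still needs to be followed for GI2 until the achievement of this endpoint or until he/she completes the study". For patients discharged before a first bowel movement, site staff communicate "with the patient daily up to and including Day 10 to record when the first bowel movement occurred".

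**The concern.** A patient with no bowel movement has no bowel-movement time. Under SAP 5.1 read literally, that patient is not in the mITT. Under the first rule of SAP 9.1 the GI2 time is missing and, with SAP 6.4, the patient drops out of the analysis. Under the second rule the patient stays and is censored. SAP 9.1 names both cases but does not say how a blank time is assigned to one or the other.

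If the literal rule were programmed, inclusion in the primary analysis would depend on the outcome. RMST would be too low to the extent that those removed are non-achievers, and the contrast between doses could move in either direction. A larger sample would not remove that bias.

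The missing sentence is also too wide for its own endpoint. If one event's time is unrecorded but is known to precede the other event, the GI2 time is simply the later one, yet SAP 9.1 calls it missing.

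**Working it through.** **1. The rules applied to five kinds of patient**

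| Patient | SAP 5.1 read literally | SAP 9.1, missing rule | SAP 9.1, censoring rule |
|---|---|---|---|
| Followed to 240 h, a component never occurs or is never recorded later | out | missing | censored |
| Withdrawn before a component occurs | out | missing | censored at last assessment |
| GI2 recorded after 240 h | in | not missing | censored (also SAP 13.2) |
| One time unrecorded, other event known to be later | out | missing | not applicable; GI2 time is known |
| Event occurred, time unrecorded, GI2 time not determinable | out | missing | not applicable; event occurred |

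The rules collide in the first two rows. In the third, even the literal reading keeps the patient.

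**2. The plan's sample size**

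Inputs from protocol 9.2: 2-sided 0.05, 80% power, contrast (-3, -1, 1, 3), about 20% censored within 240 h, differences d of 24 h (n = 44) and 18 h (n = 85). The Weibull parameters are not given.

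With equally spaced RMSTs the contrast equals 3d + d/3, that is 80 h and 60 h. Then n = (1.96 + 0.84)² × (9V1 + V2 + V3 + 9V4) / (3d + d/3)², with V the per-patient variance of RMST in each group. Assuming shape 3 and placebo RMST 120 h gives 45.1 and 84.0, close to 44 and 85, with simulated power of 79% and 80%. Other assumed parameters give quite different n, so the figures are attainable but cannot be reproduced uniquely. The calculation keeps censored patients.

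**3. Bias under the literal rule**

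All rates here are assumptions. Let p be the share not achieving GI2 by 240 h, m the mean among achievers, and suppose non-achievers are followed to 240 h. True RMST = (1 - p)m + 240p. Take m = 120 h on placebo and 96 h on 5 mg.

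- Placebo 10%, 5 mg 5%: (108 + 24) - (91.2 + 12) = 132.0 - 103.2 = 28.8 h.
- Placebo 5%, 5 mg 10%: (114 + 12) - (86.4 + 24) = 126.0 - 110.4 = 15.6 h.

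If no late GI2 is recorded, all non-achievers are deleted and both cases report 120 - 96 = 24 h.

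If half of the non-achievers have a GI2 recorded after 240 h, those stay and are censored. Their share among retained patients is 0.05/0.95 = 0.0526 when p = 10%, and 0.025/0.975 = 0.0256 when p = 5%. RMST is m + share × (240 - m).

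- 10%/5%: (120 + 0.0526 × 120) - (96 + 0.0256 × 144) = 126.3 - 99.7 = 26.6 h.
- 5%/10%: (120 + 0.0256 × 120) - (96 + 0.0526 × 144) = 123.1 - 103.6 = 19.5 h.

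The literal rule understates the effect in the first case and overstates it in the second.

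**4. Power, with censoring independent of outcome**

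These are Kaplan-Meier RMST simulations with Weibull shapes 2 to 3 and placebo RMST 88 to 126 h, all assumed. Deletion removes every patient without an observed GI2 by 240 h.

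| Setting | Censored patients kept | Deleted |
|---|---|---|
| 44 per group before deletion, 24 h, unstratified | 79-82% | 72-74% |
| 85 per group before deletion, 18 h, unstratified | 80-81% | about 73% |
| 50 randomized per group, 24 h, stratified T, equal strata | 82-86% | 75-83% |
| Same, strata 20/60/20 | 70-76% | 64-74% |
| 85 randomized per group, 18 h, stratified T, equal strata | 79-81% | 69-76% |
| Same, strata 20/60/20 | 68-72% | 60-67% |

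The loss is 2 to 10 points with the stratified T of SAP 9.1.1. The lower level with unequal strata appears under both rules and comes from the equal stratum weights in T, which is a separate matter.

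On counts, if the whole 20% had no GI2 time, 50 would leave 50 × 0.8 = 40 and 85 would leave 68. If instead 20% of censoring times fall below 240 h, 45-46 and 76-79 remain.

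**The case against.** The case for the plan is strong on intent. The added clause follows the words for the primary endpoint and can be read as merely describing it. SAP 6.4 applies unless otherwise noted, and the censoring sentence is such a note. Protocol 9.2 assumes about 20% censoring. SAP 9.1.2 and 9.3.10 tabulate GI2 as yes or no, SAP 9.3.5 has an mITT category for patients who did not achieve GI2, and the sample code in SAP 13.2 takes censoring status as an input. SAP 7.1 tabulates reasons for exclusion from the mITT, which would expose wrongful exclusions. All of this stands and makes censoring the better reading. It does not supply the missing assignment rule or cure the over-wide missing sentence, and a disposition table detects an error only after the population is built.

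A reader might infer more than the documents support:

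- That the plan excludes all non-achievers. It does not: protocol 8.1.1.1 follows patients for GI2 after they stop treatment, and a GI2 recorded after 240 h has all three times. Scheduled contact after discharge ends at Day 10, so some late bowel movements may go unrecorded; the share is unknown.
- That neither document distinguishes the two cases. SAP 9.1 names both, and protocol 9.4.5.1 contains no conflict.
- That RMST must be too low in every arm. If an event occurred and its time was lost for reasons unrelated to timing, deletion does not lower RMST.
- That the minimum of 44 per group would be missed. That needs the worst case of 40 left out of 50.

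**Conclusion.** The ambiguity is real and sits in the definition of the primary population and endpoint. Censoring is evidently intended, and the literal reading is possible but not forced. The harm is conditional on a programmer applying that reading. It would then be chiefly bias of unknown direction: in the illustrations, 28.8 h reported as 24 to 26.6 h, or 15.6 h reported as 19.5 to 24 h, depending on whether none or half of the non-achievers have a late recorded time. The power loss of about 2 to 10 points is secondary. Non-achievement rates, achiever means, Weibull parameters and stratum shares are assumptions, since the documents give none. This should be fixed before database lock and unblinding.

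**What to change.** **SAP 5.1.** Restore the protocol 9.3 wording. State that mITT membership does not require an observed food or bowel-movement time, and that a recorded finding of not yet achieved counts as a postbaseline assessment.

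**SAP 9.1.** State that a component that has not occurred by 240 h is not missing: the patient stays in the mITT and is censored at 240 h if followed to then, otherwise at the last nonmissing assessment. Limit missing to an unknown end-of-surgery time, or to an event known to have occurred at an unknown time when GI2 cannot be determined from the other, later component.

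**Remaining class.** Prespecify one handling. Assigning a bounded time is one option among several, but it is single imputation, and SAP 6.4 and protocol 9.4 rule out imputing or replacing missing data. Either write it as an explicit, justified exception to both, or use it only as a sensitivity analysis.

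**Cost.** SAP text and derivation rules only; no new data or patients. Protocol 9.4 has the SAP finalized before database lock and requires changes from the protocol analyses to be justified there, which matters only if a bounded time enters the primary analysis.
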